#### *Contamination with intervention materials (control hospitals)*

- The explicit use of materials specially designed for, or used in, the intervention in in-service training activities.

The violations will be detected through the continuous monitoring system that will be established at the Data Unit at CLAP. If a protocol violation is detected at the intervention hospitals, coordinators in Argentina and Uruguay will be in charge of contacting the opinion leaders' team in order to assess the problems to comply and establish corrective and preventive measures. In control hospitals, assessment of the in-service training activities will be done through the coordinators and data supervisors on a quarterly basis.

This list of protocol violations is provisional. The final list will be developed after the refinement of the intervention, following the formative research.

#### ***4.7. Adverse Events***

##### Adverse events in health providers (study subjects)

Although we do not expect adverse events in the study subjects, it might be possible that the active participation (or not participation) of the health providers in the intervention could originate conflicts among some of them, or with the hospital authorities, related to the implementation of the new guidelines in clinical care. It also might be possible that some women had conflicts with the birth attendants related to the use (or non-use) of the practices recommended in the new guidelines. These kinds of conflicts could be interpreted as adverse events if they led to

- loss of job positions or
- malpractice lawsuits.

CLAP study coordination will monitor the changes in the health providers' staff composition on a weekly basis. If any health provider resigned or was fired, a specific questionnaire will be completed considering the motives (from the hospital and the subject's point of view). Reports will be sent to the corresponding staff at the Data Center and National Institute of Child Health and Human Development (NICHD) within 7 days of identification. CLAP study coordination will ask the Head of the Obstetric Department in each hospital to report all malpractice lawsuits directed toward the department's health providers. The coordinators will also specifically address this issue with the Head of the Department on a quarterly basis. If any health provider received a malpractice lawsuit, resigned or was fired, a specific questionnaire will be completed considering the terms of the suit and the time period of the event that originated it. Reports will be sent to the corresponding staff at the Data Center and NICHD within 7 days of identification.

##### Adverse events in women and children

Although women and their offspring are not subjects in this study, they are the ultimate beneficiaries of the health practices promoted in the intervention. We do not expect adverse events associated with the behavioral intervention on health providers. However, we will continuously monitor in-hospital maternal deaths and early neonatal deaths up to discharge from hospital. The routine data forms of the PIS include maternal and neonatal status at discharge (alive, death), and they will be monitored on daily basis through the data collectors during all the study period. To be able to assess women who are readmitted, the Head of the Department will be instructed to report any maternal death occurring in the hospital, also on a daily basis.

In case of a maternal death, a specific case report form will be completed with the following information: date, time of onset; clinical history; medical management, including rationale; pertinent laboratory tests; relevant past medical history; autopsy report or expectation of an autopsy; location/study center; reporting physician; verification of notification to IRB, Data Safety and Monitoring Board (DSMB), and the Data Center (see appendix 3 for the form).

The death will be reported to the corresponding staff at the Data Center, NICHD, and IRB within 2 days of the occurrence.

To monitor neonatal deaths, monthly monitoring reports on the number of in-hospital early neonatal death (up to 7 days of life) and number of live births in the same period will be produced and sent to the DSMB.

## 5. Measurement Methods

---

### *5.1. Description of Questionnaires*

#### *5.1.1. Clinical data collection instruments*

Although the hospital will be the unit of analysis, we will collect patient data in order to obtain high quality data. We will collect data on primary and secondary outcomes and on potential confounders or effect modifiers. We will also collect data for safety monitoring (neonatal morbidity and mortality and maternal mortality). For clinical data there are 4 data collection forms (see appendix 6). CLIN1 form will collect data at the time of delivery, and ALTA1 will collect data on events from delivery to postpartum discharge. CLIN1 and ALTA1 forms will be used at data collection periods I and III. CLIN2 and ALTA2 will be used in data collection period II and IV (see figure 1 and section 5.2). The only difference between these two sets of forms is that CLIN1 and ALTA1 collect data on post-partum blood loss, while CLIN2 and ALTA2 do not.

All the hospitals in the project use a standard perinatal clinical history form (PIS form). This form registers the data of the obstetric history, prenatal care, labor, delivery, and neonatal outcomes. The additional information is recorded in other instruments and varies according to the hospital (i.e. laboratory results, ultrasound, etc.). This form was developed by CLAP in 1984 as a part of technical cooperation provided by the Centre to the countries in Latin America and the Caribbean. Some, but not all of the hospitals in the study enter the data in this document format using a computer program that was also developed by CLAP.

The forms for the data collection (CLIN1 and ALTA1) have 38 variables; only 11 of those variables are not in the perinatal clinical history of PIS. These variables are not registered in any other data collection instrument in the clinical record. These are variables with information that should be recorded immediately after delivery (active management of the third stage, retain placenta, second and third degree tears, etc.), and because deliveries occur 24 hours/7 days a week, the data must be collected by personnel that are always present in the delivery room, such as birth attendants or nurses. To obtain these additional data, CLAP will implement a modified version of the PIS clinical record containing the additional variables during the data collection periods. This approach will reduce to a minimum the extra activities associated with data collection that the birth attendant will need to perform during the study. The alternative to this option would be the introduction of a new paper data collection form, but as mentioned before, most of the information will be copied from the PIS form anyway.

### *5.1.2. Questionnaires to birth attendants*

A self administered "Readiness Questionnaire" (RQ) (Appendix 6 for the form and Appendix 5 for the informed consent) was designed to assess physicians' and midwives' perceived current practices in managing the third stage of labor and episiotomy practices; their beliefs in and perceived barriers to conforming to the evidence-based guidelines; interventions they are receptive to (e.g., feedback, academic detailing); and their commitment to improvement (Main et al., 1995).

### *5.1.3. Process data*

Data will also be collected to monitor the process of the intervention. A description of forms and methods for process measures can be found in section 5.6..

## ***5.2. Schedule of Data Collection***

Table 4 presents the components and the schedule for data collection in the project. There are three different sets of data to be collected, and the data collection system will be different for each one. These are

1. clinical outcomes,
2. readiness to change questionnaire to health providers, and
3. process measures.

Clinical outcomes and readiness to change questionnaire includes the primary and secondary outcomes of the project and will be measured in all participating hospitals (intervention and control arm). Process measures will be used to explore aspects of the intervention implementation, and they will be measured only in the intervention hospitals.

Clinical data will be collected in four periods, and each will be 1 year apart (Table 4):

- Period I. Baseline data collection: before randomization in the preparatory phase, for primary and secondary outcomes.
- Period II. Mid-intervention data collection: immediately before the implementation of the guidelines, for primary outcomes only.
- Period III. Main post-intervention data collection: immediately following the maintenance component of the intervention, for primary and secondary outcomes.
- Period IV. Second post-intervention data collection: 1 year after the main post-intervention data collection, for primary outcomes only.

Data from period I (baseline) and III will be used for the primary analyses, and include both primary and secondary outcomes. Secondary outcomes include nonroutine procedures to measure blood loss (see below). Data collection II will be used to study trends and will be limited to primary outcomes, which can be measured without interference with the clinical processes. Data collection IV will be used to measure the sustainability of the results after the end of the intervention and will also be limited to primary outcomes to avoid interference with the clinical processes.

**Table 4.** Schedule for data collection.

Project Stage	Year					hospitals	Forms	Tools for Data Entry & validation
	1	2	3	4	5			
	Preparatory Phase (Data Collection I - Baseline)	Intervention Phase (Data Collection II)	Maintenance Phase (Data Collection III and IV)	Analysis and writing- up				
Project clinical outcomes.								
Development and testing	■ ■ ■ ■ ■					24	Clinical Data Form (CLIN1, ALTA1, CLIN2, ALTA2)	Data Management Systems in hospitals
Training and implementation in Hospitals	■ ■ ■ ■ ■							
Data collection - Primary Outcomes		■ ■ ■ ■ ■						
Primary outcomes + blood loss		■ ■ ■ ■ ■						
Readiness to change						24	Readiness to change questionnaire (READY1)	Paper forms (Data entry at CLAP)
Data Collection - Providers' opinion		■ ■ ■ ■ ■						
Process measures (only intervention group)						12	To be developed	Paper forms (Data entry at CLAP) - Web Portal
Data Collection		■ ■ ■ ■ ■						

### 5.3. Questionnaire Administration

#### 5.3.1. Clinical data

Data will be carbon copy from the clinical record. See section 5.1

#### 5.3.2. Questionnaires to birth attendants

Questionnaires will be administered to all birth attendants in the participating hospitals prior to randomization (immediately after Period I) and after the end of the intervention (immediately after Period III).

#### 5.3.3. Process data

Process data will be collected during the 18 months of the intervention at the intervention hospitals. The data collector will keep a logbook including the date the feedback reports were distributed and the date, place, objectives, and number of participants in meetings where health providers discussed the guidelines. A form will be completed after each academic visit and will include the date, the length of the visit (minutes), the training of the person visited, and the material used during the visit. During the month following the end of the intervention, a questionnaire will be sent to the directors of the hospitals of the control group to estimate the diffusion activities that might have occurred. A description of forms and methods for process measures can be found in section 5.6..

## ***5.4. Collection of Biological Samples***

### ***5.4.1. Measured total blood loss (ml)***

Nurses, midwives and physicians who are a part of the teams attending deliveries at participating hospitals will be trained in post-partum blood loss measurement. Nurses and midwives will be the main persons responsible for the measurements. Both the country coordinators and the data collection supervisors will be in charge of training. A pilot study will be implemented at the pilot hospital in Montevideo (Pereira Rossell) to assess the acceptability of the measuring technique.

Measurement technique:

A plastic bag designed to collect blood (drape) will be used to collect post-partum blood loss. The drape is made of transparent plastic and will not be calibrated.

As soon as the baby is delivered, the drape is placed under the buttock. The blood is allowed to collect into the drape as long as the woman stays in the delivery bed or chair. The time of delivery and the time when the blood collection starts and finishes will be recorded. At the end of the blood collection period, the amount of blood loss will be measured by weighing the drape on a scale provided by the study and translating g to ml. The blood and collection drape will be properly disposed of once weighed and the amount of blood loss will be recorded in the CLIN1 form by the birth attendant or the nurse.

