## ***2.4.Secondary outcomes***

### *2.4.1. Clinical secondary outcomes*

- Perineal sutures rate among single vaginal deliveries.
- Incidence of postpartum hemorrhage >500ml among single vaginal deliveries.

Perineal sutures and hemorrhages will be studied to estimate the health impact of the intervention. Previous studies have established that selective use of episiotomy decreases the frequency of perineal sutures and that active management of the third stage of labor decreases hemorrhages. However, we will measure the effectiveness of their use in the context of our study.

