#### ***3.2. Inclusion and Exclusion Criteria***

##### *3.2.1. Inclusion criteria for hospitals*

Hospitals will be invited to participate in the study if they fulfill the following criteria:

- have an Institutional Review Board (IRB), or existing committee which could serve as such, or have an agreement with an IRB which reviews the research protocols implemented in the hospital;
- have at least 500 vaginal deliveries per year;
- do not have a explicit policy for selective episiotomy and for active management of third stage of labor; and
- consent to participate in the study.

Those preselected hospitals will perform a baseline data collection (see section 5.2). . According to the results of the analysis of the baseline data collection, hospitals will be excluded if the episiotomy rate is low or the rate of active management is high, according to the following cut-off points:

- Episiotomy rate in primiparous women with spontaneous vaginal deliveries below 70 %
- Rate of active management of third stage of labor over 15%

Because these hospitals do not have a policy for selective episiotomy or active management, it is expected that none of them will be excluded by this criteria. The sample size of the study was increased to allow for exclusions (see section 10.3).

---

1 This figure was selected based on a survey in 38 hospitals in Argentina. This study showed that the episiotomy rate was above 70% in 90% of the hospitals in the survey (Althabe et al., 2002).

2 A survey in 23 hospitals in Argentina and Uruguay showed an average rate for active management of the third stage of labor of 5%.

We interviewed the Head of the Obstetrical Department from 23 potentially eligible hospitals during the month of June 2000. Twenty-one confirmed that they were performing episiotomy routinely among primiparae, and 21 reported that expectant management during third stage of labor was the standard form of care (expectant management is defined as “a hands-free policy” during third stage of labor until the placenta is expelled: no use of uterotonics or special maneuvers).

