### ***5.5.2. Secondary outcomes***

#### ***5.5.2.1. Clinical secondary outcomes***

- Perineal sutures:

Number of women with at least one perineal suture among single vaginal deliveries.

- Postpartum hemorrhage >500ml:

Number of women with measured total blood loss >500ml among single vaginal deliveries

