### ***10.3. Sample Size***

A preliminary analysis of 1995-98 PIS data from 22 Argentinean hospitals showed a baseline frequency of episiotomies among vaginal deliveries of 42%, with a standard deviation of 11%. To protect against changes in the standard deviation (Lomas et al., 1991), we have based our sample size calculations on a standard deviation of 15%. Thus, we will need 18 hospitals (9 intervention and 9 control) to identify a decrease of episiotomy rates from 40% to 20%, with a 0.05 significance level and a 80% power. Our previous analyses of PIS data have shown that about 25% of deliveries are among primiparae, and 75% among multiparae. A reduction of the general episiotomy rate from 40% to 20% could be achieved by reducing the rate among primiparae from 80% to 40%, and the rate among multiparae from 26% to 13%. The rates after the intervention would be similar to the rates achieved in a previous trial (Argentine Episiotomy Trial Collaboration Group, 1993) and are thus potentially attainable. However, the sample size of 18 hospitals will allow us to identify a smaller decrease of episiotomy rates among primiparae vaginal deliveries, from 80% to 60%, with a 0.05 significance level and a 80% power. Assuming a baseline frequency of perineal sutures among primiparae of 85% with a standard deviation of 15%, our sample size of 18 hospitals will give us a power of 80% to identify a reduction of frequency of perineal sutures to 65%, with a 0.05 significance level.

We expect the use of oxytocin during the third stage of labor to increase from 10% to 50%. However, our sample size will allow us to detect smaller changes. Assuming a baseline frequency of injections of oxytocin of 10% and a standard deviation of 5%, the sample size of 18 hospitals will give us a power higher than 95% to identify an increase of use of oxytocin from 10% to 20%, with a 0.05 significance level. Assuming a baseline PPH incidence rate of 15% and a standard deviation of 5%, the sample size of 18 hospitals will give us a power of

84% to identify a reduction from 15% to 8%, and a power of 56% if the reduction were from 15% to 10%.

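### Postpartum hemorrhage above 500 ml is counted over an open-ended collection period that the intervention could plausibly shorten; a common weighing time is needed

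*Protocol*

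**What the plan says.** Section 5.4.1 of the protocol gives the start of collection as "As soon as the baby is delivered, the drape is placed under the buttock" and its end as "The blood is allowed to collect into the drape as long as the woman stays in the delivery bed or chair". There is no fixed or minimum duration. The drape carries no calibration marks and is weighed once, when collection ends. The section adds that "The time of delivery and the time when the blood collection starts and finishes will be recorded".

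Section 5.5.2.1 defines the secondary outcome as "Number of women with measured total blood loss >500ml among single vaginal deliveries". It gives no period over which the loss is counted.

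Section 2.4.1 gives the outcome its role: "Perineal sutures and hemorrhages will be studied to estimate the health impact of the intervention". The same section states that "Previous studies have established that selective use of episiotomy decreases the frequency of perineal sutures". Section 10.3 gives the trial's power among primiparae to "identify a reduction of frequency of perineal sutures to 65%, with a 0.05 significance level", from a baseline of 85%. The third-stage care that the intervention seeks to replace is described in section 3.2.1 as hands-free "during third stage of labor until the placenta is expelled: no use of uterotonics or special maneuvers".

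Section 10.5 compares hospital percentages after the intervention by t-test and compares baseline-to-follow-up ratios. Neither uses collection time.

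**The concern.** A cumulative volume judged against a fixed threshold needs a common observation time. Here that time ends when the woman leaves the bed, which happens after randomization and after the practices the trial tries to change. A woman who needs no perineal repair, or whose third stage is shorter, may leave the bed earlier and have less blood captured. Any such shortening would lower the measured rate in the intervention hospitals, which is the direction the trial hypothesizes, without any change in bleeding.

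The recorded times would reveal a difference in duration between arms but could not repair it. With one weighing of an uncalibrated drape, the volume at a common time cannot be reconstructed. Adjusting for a duration that was itself altered after randomization is open to bias. The rule therefore has to be right before data collection starts.

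At stake is the interpretation of one of the two clinical outcomes meant to show health impact.

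**Working it through.** **1. The plan's own figure.** Inputs from section 10.3: baseline hemorrhage 15%, between-hospital SD 5%, 9 hospitals per arm, alpha 0.05 (taken as two-sided and as applying to this outcome). Power = Φ(Δ / (SD·√(2/9)) − 1.96).
- 15% to 8%: 7 / (5 × 0.4714) = 2.970, and Φ(1.010) = 84.4%. The plan states 84%.
- 15% to 10%: 5 / 2.357 = 2.121, and Φ(0.161) = 56.4%. The plan states 56%.

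The stated power reproduces. It does not depend on the collection window. The 5-point target serves below as a yardstick.

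**2. Inputs for the illustration.**
- From section 10.3: 15% above 500 ml. Episiotomy falling from 40% to 20% means 20% of women newly spared one. Oxytocin rising from 10% to 50% means 40% of women newly given it.
- Assumed, with no source in the protocol: lognormal blood loss, a median of 200 to 300 ml, and a shorter stay that captures a fraction r = 10% or 20% less blood. True loss is the same in both arms.

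**3. Chance that an affected woman is counted.** The SD on the log scale is σ = ln(500/median) / 1.0364, where 1.0364 is the 85th percentile of the standard normal. The chance of a measured loss above 500 ml is P = 1 − Φ([ln(500/(1−r)) − ln(median)] / σ).

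| Median (ml) | σ | P, r = 10% | P, r = 20% |
|---|---|---|---|
| 200 | 0.884 | 12.39% | 9.87% |
| 250 | 0.669 | 11.62% | 8.53% |
| 300 | 0.493 | 10.56% | 6.82% |

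**4. Apparent fall in the intervention arm** = (15% − P) × share of women affected.
- 20% affected: from (15 − 12.39) × 0.2 = 0.52 to (15 − 6.82) × 0.2 = 1.64 points.
- 40% affected: from 2.61 × 0.4 = 1.04 to 8.18 × 0.4 = 3.27 points.

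**5. What that does to the test.** This uses a two-sided t-test on hospital percentages with SD 5%, no true effect, and a noncentral t with the falls above. The chance of a significant result, nominally 5%, becomes:

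| Share affected | 9 per arm | 12 per arm |
|---|---|---|
| 20% | 5.5% to 10% | 5.7% to 12% |
| 40% | 7% to 26% | 8% to 34% |

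The upper ends need the 20% capture loss and the 300 ml median together.

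**The case against.** The strongest objection is that the protocol never says what determines time in the delivery bed and gives no durations. The link from fewer repairs or a quicker third stage to a shorter stay is an inference. This stands, and it is why the point is put as a possibility. A reader might infer that the protocol builds in a false reduction; the documents do not support that.

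The size also rests on assumed inputs. The model takes the same proportion from every affected woman, yet a woman who bleeds heavily may be kept in bed longer, so that loss near and above 500 ml is captured more fully. Being spared an episiotomy does not mean having no suture, since tears still occur. Both considerations point to a smaller effect than shown. A reader could reach much larger falls by applying the capture loss to every woman in the intervention arm, but nothing in the protocol suggests that all would be affected.

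It might also be argued that differing bed stays add noise between hospitals. Blood loss is measured the same way in Periods I and III, and section 10.5 compares baseline-to-follow-up ratios, so stable hospital differences largely cancel there. That part is not pressed. The baseline does not remove a shortening that appears only after the intervention.

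Finally, collection times are recorded, and how they are analyzed may properly be left to the statistical analysis plan. That is fair, but the missing time window is a measurement rule and cannot be supplied at analysis.

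**Conclusion.** The point holds as a weakness in how a secondary outcome is measured. The protocol compares a cumulative volume with a fixed cut-off over a period that is not common to all women and that the intervention could plausibly shorten. Neither the baseline comparison nor the recorded times remove this.

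The size is unknown. The illustration gives an apparent fall of 0.5 to 3.3 points if 20% to 40% of women have 10% to 20% less blood captured. That is below the smaller 5-point target, but at its upper end it is enough to cloud the reading of a modest reduction. It rests on an assumed lognormal shape, median and capture loss, and on the inferred link to bed time. The two primary outcomes and the stated power figures are not called into question. The change is worth making because it is cheap and cannot be made afterwards.

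**What to change.** Before Period I, state in section 5.4.1 and in the manual of operations one common time after birth at which the drape is weighed, in both arms and in every period in which blood loss is measured. In section 5.5.2.1, define hemorrhage above 500 ml on that weight, and call it loss up to that time rather than total loss.

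Set the time short enough that nearly all women are still in the delivery bed, including those with no suture and with active management. Setting it from usual care alone would leave early leavers in the intervention arm truncated. The pilot planned in section 5.4.1 could collect bed times for this purpose, provided it covers women managed both ways. Weigh the drape of any woman who leaves earlier on leaving, flag her from the recorded times, and report the number of such women and the collection time by arm and period.

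The cost is a sentence or two in each place. The downside is that blood lost after the common time is not counted. The absolute rate may then be lower than the assumed 15% baseline, and the power statement for this outcome should be revisited once the time is set. This is a measurement rule only and changes no care.
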